2.2.3.2 Azacitidine Clinical Experience

A randomized, open-label, controlled trial carried out in 53 U.S. sites compared the safety and efficacy of SC azacitidine plus supportive care with supportive care alone ("observation") in subjects with any of the 5 French – American – British subtypes (FAB) of MDS: Refractory Anemia (RA), RA with Ringed Sideroblasts (RARS), RA with Excess Blasts (RAEB), RAEB in Transformation (RAEB-T), and Chronic Myelomonocytic Leukemia (CMMoL). Subjects with acute myelogenous leukemia were not intended to be included. Baseline patient and disease characteristics of the 2 groups were similar. Azacitidine was administered at a SC dose of 75 mg/m² daily for 7 days every 4 weeks. The dose was increased to 100 mg/m² if no beneficial effect was seen after 2 treatment cycles. The dose was decreased and/or delayed based on hematologic response or evidence of renal toxicity.

The ORR (CR + Partial Remission [PR]) of 15.7% (14 out of 89) in azacitidine-treated subjects without AML (16.2% for all azacitidine randomized subjects including AML) was statistically significantly higher than the response rate of 0% in the observation group (p < 0.0001). The majority of subjects who achieved either CR or PR had either 2 or 3 cell line abnormalities at baseline (79%; 11 out of 14) and had elevated bone marrow blasts or were transfusion dependent at baseline.

Subjects in the observation group who crossed over to receive azacitidine treatment (47 subjects) had a response rate of 12.8%.

Protocol Number: 20200392

Date: 28 April 2022 Page 36 of 149

Additionally, a multi-center, open-label, single-arm study of 72 subjects with RAEB, RAEB-T, CMMoL, or AML was also carried out. Treatment with SC azacitidine resulted in a response rate (CR + PR) of 13.9%, using criteria similar to those described above. The mean and median duration of clinical response of PR or better was estimated as 810 and 430 days, respectively; 80% of the responding subjects were still in PR or better at the time of completion of study involvement.

In another open-label, single-arm study of 48 subjects with RAEB, RAEB-T, or AML, treatment with IV azacitidine resulted in a response rate of 18.8%, again using criteria similar to those described above. The mean and median duration of clinical response of PR or better was estimated as 389 and 281 days, respectively; 67% of the responding subjects were still in PR or better at the time of completion of treatment. Response occurred in all MDS subtypes as well as in subjects with adjudicated baseline diagnosis of AML in both of these studies. Azacitidine dosage regimens in these 2 studies were similar to the regimen used in the controlled study.

Benefit was seen in subjects who did not meet the criteria for PR or better but were considered "improved". About 24% of azacitidine-treated subjects were considered improved, and about 2/3 of those lost transfusion dependences. In the observation group, only 5 out of 83 subjects met criteria for improvement; none lost transfusion dependence. In all 3 studies, about 19% of subjects met criteria for improvement, with a median duration of 195 days. Response rate estimates were similar regardless of age or gender.

Azacitidine is commercial grade; refer to USPI for additional information.

Refer to the regional manufacturer package insert for additional information.

2.3 Benefit/Risk Assessment

Based on early evidence of clinical activity from the FIH study (20150161), nonclinical toxicity studies in AMG 176, and clinical safety experience, the overall benefit/risk profile supports the further clinical development of AMG 176 in combination therapy for subjects with HR-MDS/CMML. Clinical signs and symptoms, along with other safety laboratory parameters, will be monitored during the study and at the appropriate time points to ensure subjects' safety.

The following benefit/risk assessment supports the conduct of this clinical trial.

Reference should be made to the Investigator's Brochure for further data on AMG 176.

Protocol Number: 20200392

Date: 28 April 2022 Page 37 of 149

2.3.1 Key Benefits

As AMG 176 is in early development and clinical experience is limited, key benefits are still being evaluated. As of 23 April 2020, 17 subjects with R/R AML were enrolled in Part 3. Of these 17 subjects, 2 subjects in dose escalation have achieved incomplete Count Recovery (CRi), with AMG 176 treatment at the 60 mg/m² and 120 mg/m² QD2 dose levels. One subject achieved a PR at the 60 mg/m² QD2 dose. Since the 23 April 2020 data cut-off, additional subjects have been enrolled and analysis is ongoing. There have been no additional risks identified.

Preclinical data identified a synergistic effect with AMG 176 when given in combination with the HMA decitabine or venetoclax that resulted in an increase in anti-leukemic activity (see Section 2.2.2.1). Based on preclinical data, AMG 176 in combination with azacitidine therapy, a similar HMA, is anticipated to provide a new treatment option with the potential for better disease control with more Durable Responses (DR) that will lead to improved clinical outcomes for subjects with MDS/CMML.

2.3.2 Key Risks

At this time, there is limited clinical experience with AMG 176 in humans. Based on biological plausibility, nonclinical toxicity studies of AMG 176, and clinical safety experience, Tumor Lysis Syndrome (TLS), increased troponins, neutropenia, nausea, vomiting, and diarrhea have been determined to be identified risks.

Tumor Lysis Syndrome

Administration of AMG 176 has been associated with TLS with a fatal outcome. Subjects with a high tumor burden or compromised renal function (eg, International Staging System [ISS] Stage II/III) may be at elevated risk for TLS. The risk of TLS may increase in the setting of combinational therapy with azacitidine due to the anticipated increase in anti-leukemic activity. To mitigate the risk of TLS, blood chemistry (potassium, uric acid, phosphorus, calcium, and creatinine) must be assessed in all subjects and any pre-existing abnormalities must be corrected prior to starting treatment with AMG 176. In addition, subjects must be appropriately hydrated prior to each dose of AMG 176. Refer to Section 11.9 (Appendix 9) for specific recommendations regarding the mitigation and management of TLS.

Increased Troponin

Administration of AMG 176 has led to elevations of serum troponins. The exact cause and clinical effects of troponin increases observed during the use of AMG 176 are not

Protocol Number: 20200392

Date: 28 April 2022 Page 38 of 149

known. A cardiac monitoring plan has been implemented to mitigate the risk of troponin elevations and potential for cardiac toxicity. Refer to Section 11.10 (Appendix 10) and Section 11.11 (Appendix 11) for specific information regarding the cardiac monitoring plan and dose modification guidelines, respectively.

Potential Risks

In addition to the identified risks listed above, potential risks for AMG 176 based on nonclinical findings **include** reproductive toxicity-male, hepatobiliary toxicity, and cardiovascular toxicity (for details, see Section 2.2.2.3). In addition, bone marrow toxicity has been observed in non-clinical studies. While neutropenia has been identified as a risk, anemia and thrombocytopenia due to bone marrow toxicity remain a potential risk. Additional DDI risk is unknown at this time. Enrolled subjects will be advised on the risk associated with AMG 176 administration and signs and symptoms of the risks, along with other safety labs, will be monitored during the study and at the appropriate time points to ensure subjects' safety.

Please refer to the AMG 176 Investigator's Brochure for further description of potential risks.

There is significant clinical experience with azacitidine and it has an acceptable safety profile. Hematological toxicity, hepatotoxicity, and TLS are associated with azacitidine. Tumor Lysis syndrome is an identified risk and bone marrow toxicity and hepatobiliary toxicity are potential risks for AMG 176. The incidence and/or severity of these risks may increase when azacitidine and AMG 176 are given in combination. Refer to Section 6.2 for dose modification guidelines for both AMG 176 and azacitidine, as well as the approved product label of azacitidine.

Co-administration of AMG 176 with azacitidine is unlikely to result in DDIs based on in vitro studies (refer to azacitidine USPI and AMG 176 Investigators Brochure).

The above benefit risk assessment supports the conduct of this clinical trial. Reference should be made to the Investigator's Brochure for further data on AMG 176, and the respective Prescribing Information for further data on azacitidine.

3. Objectives and Endpoints/Estimands

| Objectives | Endpoints | | |
|---|-----------|--|--|
| Primary | | | |
| Part 1A – QW Monotherapy (Dose Exploration) | | | |

Protocol Number: 20200392

Date: 28 April 2022 Page 39 of 149

 Evaluate the safety and tolerability of AMG 176 once weekly (QW) monotherapy in subjects with R/R higher risk myelodysplastic syndrome (HR-MDS) Incidence of dose limiting toxicities (DLTs), treatment-related, treatment-emergent adverse events and clinically significant changes in vital signs, electrocardiogram (ECGs), and clinical laboratory tests

Part 1B – QW Combination Therapy (Dose Exploration)

- Evaluate the safety and tolerability of AMG 176 in combination with azacitidine in subjects with R/R HR-MDS and determine the Optimal Biological Dose (OBD) and Minimum Safe and Biologically Effective Dose (MSBED) of AMG 176 in combination with azacitidine
- Incidence of DLTs, treatment-related, treatment-emergent adverse events and clinically significant changes in vital signs, ECGs, and clinical laboratory tests

Part 2 – QW Combination Therapy (Dose Expansion)

- Evaluate the preliminary efficacy of AMG 176 in combination with azacitidine in subjects with R/R HR-MDS/CMML in:
 - HMA Failure, Venetoclax-Naïve
 - HMA Failure, Venetoclax-Exposed
- To assess the preliminary efficacy of AMG 176 in combination with azacitidine in subjects with Newly Diagnosed MDS/CMML
- Overall response rate (ORR), according to the Uniform Response Criteria for Myelodysplastic/ Myeloproliferative Neoplasms (MDS/MPN), including:
 - Complete Remission (CR)
 - Partial Remission (PR)
 - Marrow CR
 - Cytogenic response

Secondary

Part 1A – QW Monotherapy (Dose Exploration)

- Evaluate preliminary efficacy of AMG 176 QW when given as monotherapy in R/R MDS/CMML
- Overall response according to the Uniform Response Criteria for MDS/MPN, Event-Free Survival (EFS), time to response, and Duration of Response (DOR)
- Evaluate the pharmacokinetics (PK) of AMG 176 when administered as monotherapy
- PK parameters for AMG 176 including, but not limited to, maximum observed concentration (C_{max}), area under the concentration-time curve (AUC), clearance (CL), and half-life (t_{1/2})

Part 1B – QW Combination Therapy (Dose Exploration)

- Evaluate preliminary efficacy of AMG 176 QW in combination with azacitidine in R/R MDS/CMML
- Overall response according to the Uniform Response Criteria for MDS/MPN, EFS, time to response, and DOR

Protocol Number: 20200392

Date: 28 April 2022 Page 40 of 149

| Evaluate the PK of AMG 176 and azacitidine when administered in combination | PK parameters for AMG 176 and azacitidine including, but not limited to, C _{max} , AUC, CL, and t _{1/2} |
|---|---|
| Part 2 – QW Combination Therapy (Dose E | Expansion) |
| Evaluate the preliminary efficacy of AMG 176 in combination with azacitidine in subjects with R/R HR-MDS/CMML in: HMA Failure, Venetoclax-Naïve HMA Failure, Venetoclax-Exposed To assess the preliminary efficacy of AMG 176 in combination with azacitidine in subjects with Newly Diagnosed MDS/CMML | Time to transformation to Acute Myeloid Leukemia (AML) Duration of Response (DOR) Overall Survival (OS) Time to Next MDS Treatment (TTNT) EFS |
| Evaluate the PK of AMG 176 and azacitidine when administered in combination | PK parameters for AMG 176 and azacitidine including, but not limited to, C _{max} , AUC, CL, and t _{1/2} |

4. Study Design

4.1 Overall Design

This study is a phase 1 clinical trial designed to assess the safety, tolerability, and efficacy of AMG 176 in combination with the 7-day regimen of azacitidine for the treatment of HR-MDS/CMML. Subjects will be treated with IV AMG 176 and IV or SC azacitidine. The study consists of 2 parts.

4.1.1 Part 1 – Dose Escalation/Determination of Optimal Biological Dose (OBD) and Minimal Safe and Biologically Effective Dose (MSBED)

In Part 1, the modified Toxicity Probability Interval (mTPI) design will be applied for dose escalation. Three dose levels of AMG 176 monotherapy will first be tested, and after the OBD is found, three dose levels of AMG 176 in combination with azacitidine will be tested.

After obtaining the monotherapy data from Part 1A, available data for monotherapy and combination therapy (with azacitidine) from the FIH study (Study 20150161) will also be leveraged to identify the MSBED for AMG 176. Dose exploration for AMG 176 in combination with azacitidine in Part 1B will then begin at the monotherapy MSBED -1 for AMG 176. The combination MSBED in Part 1B will be selected after an integrated assessment of all available clinical safety, efficacy, PK, and pharmacodynamic (PD) data for AMG 176 is performed, in order to select doses of AMG 176 that are likely to achieve the optimal benefit-risk profile.

Protocol Number: 20200392

Date: 28 April 2022 Page 41 of 149

Each dose cohort will initially enroll 3 to 4 subjects and up to 10 subjects per cohort may be enrolled. After reviewing all available safety data, dose level decisions (eg, escalation, de-escalation) will be made by the DLRT using mTPI model (Ji et al, 2010) based on all subjects that have been enrolled at the current dose. The DLRT may change the dose/dosing scheduled based on emerging data. The OBD/MSBED is defined as the minimum safe and biologically effective combination dose with a probability of DLT lower than or close to a targeted toxicity probability of 0.2.

Dose escalation is considered complete if one of the following rules is met:

 The highest planned dose level is evaluated, OBD has not been defined, and no DLTs occur at any dose level. In this case, the Maximum Administered Dose (MAD) may be used for Part 2.

2. An OBD is identified.

Guidelines for dose level decisions can be found in Table 4-1. Details regarding the mTPI model are described in Appendix 14 (see Section 11.14).

Number of DLTs No. of DLT-evaluable^a subjects treated at current dose Escalate Stay at current dose De-escalate^b 0 1 3 ≥ **2** 6 0-1 ≥ 2 9 0-1 2 ≥ 3 10^c 0-1 2-3 ≥ 4

Table 4-1. Guidelines for Dose Level Decisions in Part 1

4.1.2 Part 2 – Dose Expansion

Upon completion of Part 1 of the study, the dose expansion phase will begin at the OBD/MSBED and drug administration schedule with the intention of confirming the safety and tolerability and determining the efficacy of AMG 176 in combination with azacitidine in not only R/R HR- MDS/CMML, but also in frontline HR-MDS/CMML. An additional 60 subjects will be enrolled in Part 2 of the study as follows:

HMA Failure Cohort: stratified by venetoclax exposure history

○ HMA Failure, venetoclax-Naïve (n = 20)

DLT = dose limiting toxicity.

^a A subject is considered DLT-evaluable if he/she experienced a DLT during the DLT evaluation period; or if he/she received 75% of the planned doses of AMG 176 and 100% of the planned doses of azacitidine, and completed the DLT evaluation period.

^b De-escalate guideline applies only when current dose level and enrollment is allowed to a lower dose level.

^c The maximum number of evaluable subjects at one dose level is 10.

Protocol Number: 20200392

Date: 28 April 2022 Page 42 of 149

- HMA Failure, venetoclax-Exposed (n = 20)
- Newly Diagnosed (n = 20) subjects will not be enrolled into this cohort until all previous cohorts have been completed and the data reviewed by the FDA.
 Toxicity will be monitored for each cohort using a Bayesian approach proposed by Thall, Simon, and Estey (1995).

The incidence of grade 3 or higher treatment-related non-hematological adverse events will be evaluated once every 5 subjects have had the chance to receive at least 1 cycle of treatment at the determined dose level for Part 2. Assuming a prior distribution of beta (1, 1), if the posterior probability that the incidence is greater than 20% is > 80% at these interim analyses, the study will stop early. The purpose of the safety interim analyses is to assess if the threshold for early termination has been reached. The stopping rules and operating characteristics are described in Table 4-2 and Table 4-3.

Number of subjectsStop study if observing this number of subjects with grade 3 or higher treatment-related non-hematological adverse event $5 \sim 6$ ≥ 2 $7 \sim 10$ ≥ 3 $11 \sim 14$ ≥ 4 $15 \sim 19$ ≥ 5 20Completes

Table 4-2. Stopping Boundary for Each Cohort in Part 2

| Table 4-3. O | perating | Characte | ristics | in | Part 2 |
|--------------|----------|----------|---------|----|--------|
|--------------|----------|----------|---------|----|--------|

| True grade 3 or higher treatment-related non-hematological adverse event rate | Probability of early stopping |
|---|-------------------------------|
| 0.10 | 15% |
| 0.15 | 32% |
| 0.20 | 51% |
| 0.25 | 69% |
| 0.30 | 82% |

Duration of Therapy

In the absence of treatment delays due to clinically significant study drug-related adverse events, treatment may continue until one of the following criteria applies:

- Clinically significant progressive disease. Subjects may continue therapy with either
 or both AMG 176 and azacitidine as long as they have stable disease, as long as, in
 the opinion of the treating physician and/or Principal Investigator (PI), the subject
 continues to derive clinical benefit and has otherwise not had an event requiring
 permanent discontinuation.
- Inter-current illness that prevents further administration of treatment.

Protocol Number: 20200392

Date: 28 April 2022 Page 43 of 149

Subject decides to withdraw from the study.

• Excess toxicity that in the opinion of the PI would present a safety risk for further participation on the study.

Subjects may receive further courses of therapy not earlier than 4 weeks from the previous course, provided the subject has recovered from myelosuppression considered to be related to chemotherapy.

A minimum of one full course (or 4 weeks from the start of therapy) will be required for a subject to be considered as having received an adequate trial to evaluate efficacy. All subjects receiving at least one dose of any of the two drugs will be considered evaluable for toxicity. Subjects achieving a partial remission or with stable disease may continue on therapy until definite evidence of disease progression.

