#### Part 2 – Dose Expansion (Not Applicable, did not enroll)

Upon completion of Part 1 of the study, the dose expansion phase will begin at the **OBD/MSBED** and drug administration schedule with the intention of confirming the safety and tolerability and determining the efficacy of AMG 176 in combination with azacitidine in not only R/R HR- MDS/CMML, but also in frontline HR-MDS/CMML. An additional 60 subjects will be enrolled in Part 2 of the study as follows:

- HMA Failure Cohort: stratified by venetoclax exposure history
  - HMA Failure, venetoclax-Naïve (n = 20)
  - HMA Failure, venetoclax-Exposed (n = 20)
- Newly Diagnosed (n = 20) subjects will not be enrolled into this cohort until all previous cohorts have been completed and the data reviewed by the FDA.
   Toxicity will be monitored for each cohort using a Bayesian approach proposed by Thall, Simon, and Estey (1995).

The incidence of grade 3 or higher treatment-related non-hematological adverse events will be evaluated once every 5 subjects have had the chance to receive at least 1 cycle of treatment at the determined dose level for Part 2. Assuming a prior distribution of beta (1, 1), if the posterior probability that the incidence is greater than 20% is > 80% at these interim analyses, the study will stop early. The purpose of the safety interim analyses is to assess if the threshold for early termination has been reached. The stopping rules and operating characteristics are described in Protocol Table 3-2 and Table 3-3.

Table 3-2. Stopping Boundary for Each Cohort in Part 2

Number of subjects	Stop study if observing this number of subjects with grade 3 or higher treatment-related non-hematological adverse event
5 ~ 6	≥ 2

<sup>a A subject is considered DLT-evaluable if he/she experienced a DLT during the DLT evaluation period; or if he/she received 75% of the planned doses of AMG 176 and 100% of the planned doses of azacitidine and completed the DLT evaluation period.

<sup>b De-escalate guideline applies only when current dose level and enrollment is allowed to a lower dose level.

<sup>c The maximum number of evaluable subjects at one dose level is 10.

Protocol Number: 20200392

Date: 10 May 2024 Page 15 of 33

7 ~ 10	≥ 3
11 ~ 14	≥ 4
15 ~ 19	≥ 5
20	Completes

Table 3-3. Operating Characteristics in Part 2

True grade 3 or higher treatment-related non-hematological adverse event rate	Probability of early stopping
0.10	15%

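### Part 2 early-stopping probabilities were computed for a check after every subject from the 5th, not every 5 subjects as the rule states, and overstate protection by up to 13 percentage points

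*Protocol*

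**What the plan says.** Protocol section 4.1.2 plans three Part 2 cohorts of 20 subjects and monitors toxicity in each cohort. The monitored event is a grade 3 or higher treatment-related non-hematological adverse event, and its incidence "will be evaluated once every 5 subjects have had the chance to receive at least 1 cycle of treatment". The prior is Beta(1,1), and "if the posterior probability that the incidence is greater than 20% is > 80% at these interim analyses, the study will stop early".

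Table 4-2 turns this into limits: at least 2 events at 5–6 subjects, 3 at 7–10, 4 at 11–14 and 5 at 15–19. At 20 the cohort completes, with no stopping limit. Table 4-3 gives early-stopping probabilities of 15%, 32%, 51%, 69% and 82% for true rates of 0.10, 0.15, 0.20, 0.25 and 0.30. It does not state the schedule of looks behind them.

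The SAP repeats the rule, the limits and the probabilities, the last under "Table 3-3. Operating Characteristics in Part 2". In both documents the limits table is titled as applying to each cohort, yet its column heading reads "Stop study if observing this number of subjects with grade 3 or higher treatment-related non-hematological adverse event".

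**The concern.** The rule and its operating characteristics have to describe the same design. Looks after every 5 subjects give three chances to stop a cohort (5, 10, 15). Looks after each subject from the 5th to the 19th give fifteen. More looks against the same limits can only raise the chance of stopping, so a table computed for one schedule cannot be right for the other.

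Table 4-3 is the only place where either document quantifies how often the Part 2 rule would stop. If it belongs to denser monitoring than the text prescribes, a reader will believe that a cohort with a 25% or 30% event rate is stopped more reliably than it would be.

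The unit is a second ambiguity. If one cohort crossing its limit stops the whole study, the probability that matters is that at least one of three cohorts triggers, and neither document gives it.

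**Working it through.** **Inputs** (Protocol section 4.1.2, Tables 4-2 and 4-3; repeated in SAP section 3.1): Beta(1,1) prior; stop if Pr(p > 0.20 | data) > 0.80; 20 subjects per cohort; no stopping at 20; a look every 5 subjects.

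**Step 1: the limits.** With x events in n subjects the posterior is Beta(1 + x, 1 + n − x). The limit is the smallest x for which Pr(p > 0.20) exceeds 0.80. Examples:

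- n = 5: x = 1 gives 0.655, x = 2 gives 0.901, so the limit is 2.
- n = 10: x = 2 gives 0.617, x = 3 gives 0.839, so the limit is 3.
- n = 15: x = 4 gives 0.798, x = 5 gives 0.918, so the limit is 5.

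This agrees with Table 4-2 at every n from 5 to 19. The limits are correct.

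**Step 2: reproduce the printed probabilities.** Let f(n, k) be the probability of reaching n subjects with k events without having stopped. Then f(n, k) = f(n−1, k)(1−p) + f(n−1, k−1)p. At each look, all probability at or above the limit is moved to stopped. With a look at every n from 5 to 19 the totals are 14.97%, 32.03%, 51.31%, 68.86% and 82.27%. All five round to the printed figures.

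**Step 3: the stated schedule, looks at 5, 10 and 15.** Worked at p = 0.30, with B the number of events in the next 5 subjects, so Pr(B ≥ 2) = 0.47178, Pr(B ≥ 3) = 0.16308, Pr(B ≥ 4) = 0.03078 and Pr(B = 5) = 0.00243:

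- Look at 5 (limit 2): 1 − 0.7⁵ − 5(0.3)(0.7⁴) = 1 − 0.16807 − 0.36015 = 0.47178. Continuing with 0 or 1 event: 0.16807, 0.36015.
- Look at 10 (limit 3): 0.16807 × 0.16308 + 0.36015 × 0.47178 = 0.19732. Continuing with 0, 1 or 2 events: 0.02825, 0.12106, 0.18159.
- Look at 15 (limit 5): 0.02825 × 0.00243 + 0.12106 × 0.03078 + 0.18159 × 0.16308 = 0.03341.
- Total: 0.47178 + 0.19732 + 0.03341 = 0.7025.

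**Step 4: all rates.**

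| True rate | Printed | Every subject, 5–19 | Looks at 5, 10, 15 | Printed minus stated schedule | Looks at 5, 10, 15, 20 |
|---|---|---|---|---|---|
| 0.10 | 15% | 15.0% | 11.5% | 3.5 points | 11.7% |
| 0.15 | 32% | 32.0% | 24.8% | 7.2 points | 25.8% |
| 0.20 | 51% | 51.3% | 40.5% | 10.5 points | 43.2% |
| 0.25 | 69% | 68.9% | 56.3% | 12.7 points | 60.7% |
| 0.30 | 82% | 82.3% | 70.3% | 11.7 points | 75.7% |

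The last column adds a look at 20 with its derived limit of 6, although Table 4-2 has none; it still does not match. Per-subject looks from the first subject do not match either (31%, 48%, 64%, 78%, 87%).

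**Step 5: chance of not stopping.** At 0.30: 100 − 70.3 = 29.7%, against 100 − 82 = 18% printed, a ratio of 29.7/18 = 1.65. At 0.25: 43.7% against 31%.

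**Step 6: if one cohort stops the study.** Assuming three independent cohorts with one common rate and looks at 5, 10 and 15, the chance that at least one triggers is 1 − (1 − 0.1147)³ = 30.6% at a rate of 0.10 and 1 − (1 − 0.4048)³ = 78.9% at 0.20.

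**The case against.** The best defence is that per-subject monitoring was intended. Table 4-2 gives a limit for every n from 5 to 19, which three fixed looks would not need, and Table 4-3 matches per-subject looks exactly. On that view no probability is wrong and one sentence is loosely worded. This may be so, but it concedes that text and table disagree. The intermediate limits could also be there only for looks that do not land exactly on a multiple of 5.

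A second point is that the text does not say outright that the count of 5 runs within a cohort, nor that accrual pauses. If it runs across two cohorts accruing alternately (an assumption), a cohort is looked at near 5, 7–8, 10, 12–13, 15 and 17–18. Stopping is then 60.8–63.8% at a rate of 0.25 and 75.2–78.2% at 0.30, so the gaps shrink to about 5–8 and 4–7 points. If looks slip to 6, 11 and 16, the figures are 56.8% and 71.1%. The size of the gap therefore depends on the reading, but none of these schedules reproduces the table. Looks at 5, 10 and 15 remain the natural reading of a rule applied to each cohort.

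Three further points stand. At 0.10 and 0.15, below the 20% threshold, less stopping means fewer false stops, so protection is overstated only at the higher rates. The study-level figures rest on independence and a common rate, and they point towards more stopping than printed. Safety is also reviewed on an ongoing basis, and the medical monitor may suspend dosing at any time, so the rule is not the only safeguard.

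**Conclusion.** The concern holds. The limits are right for the stated prior and threshold, but the printed probabilities belong to looks after each subject from the 5th to the 19th and not to the schedule in the text. Under looks at 5, 10 and 15 in a cohort of 20, the table is too high by 3.5 to 12.7 points, with the maximum at a true rate of 0.25. A cohort with a 30% event rate would run to completion 1.65 times as often as the table implies. These sizes assume independent subjects, counting within each cohort and no look at 20.

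The mismatch between study and cohort as the unit that stops is real but secondary.

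The SAP records that Part 2 did not enroll, so no subject was monitored under the rule and no result changes. The figures still stand in the SAP of 10 May 2024 and should be corrected there.

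**What to change.** Make text and table describe one schedule, in both documents:

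- If looks every 5 subjects were intended, replace the entries of Protocol Table 4-3 and SAP Table 3-3 with 11.5%, 24.8%, 40.5%, 56.3% and 70.3%, and state that the looks are at 5, 10 and 15 within each cohort.
- If per-subject monitoring was intended, keep the printed figures and change the sentence on frequency to say after each subject from the 5th to the 19th.

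In either case, add the look schedule to the table caption. State whether a crossed limit stops the cohort or the study, and align the text and the column heading with that. If it is the study, give study-level probabilities with their assumptions.

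The cost is five numbers or one sentence per document, plus a label. Under the first option the stated stopping probabilities fall at every rate, which is less protection above 20% and fewer false stops below it.
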